8.2.2 Infusion-related reactions

Infusion-related reactions are defined as hypersensitivity reactions, anaphylactic reactions and cytokine release syndrome with onset within 24 hours after the start of the UCB6114 infusion.

All potential infusion-related reactions will be identified programmatically and will then undergo medical review for confirmation based on participant characteristics and other signs and symptoms. The final assessment from the medical review will be used in the programming to ensure that all infusion-related reactions are flagged correctly in the listings and included in the relevant summaries.

Hypersensitivity reactions will be programmatically identified as any TEAE with a PT from both a narrow and broad scope search of category A terms of the 'Hypersensitivity' Standardized MedDRA Query (SMQ).

Anaphylactic reactions will be programmatically identified using an algorithmic approach based on the 'Anaphylactic Reaction' SMQ. Further details on this algorithm are given in Section 13.1. Note that if the MedDRA version is increased from 25.1 during the study, any changes to the terms included in the 'Anaphylactic Reaction' SMQ should be applied.

Cytokine release syndrome will be programmatically identified as any TEAE with a PT of 'Cytokine release syndrome' from the broad scope search of category A terms of the 'Hypersensitivity' SMQ. Since this disorder is characterized by fever, headache, tachycardia, hypotension, rash, tachypnoea and/or hypoxia, a further medical review of participants with these events occurring within 24 hours after infusion of study treatment will be performed to confirm any further infusion-related reactions.

Note that any other AEs (i.e. not identified as infusion-related reactions using the rules above) which result in a temporary interruption or permanent discontinuation of an infusion will not be considered as an infusion-related reaction.

8.3 Clinical laboratory evaluations

The use of multiple local laboratories (1 per site in the UK) in Part A of this study has meant that results have been recorded in different units and with reference to different normal ranges, and

further, for some laboratory tests, different normal ranges have been applied to males and females and age groups. As a first step to ensure comparability of laboratory results, results and normal ranges will be converted to the same International System of Units (SI) units using UCB's standard conversion factors. This will be programmed at the Study Data Tabulation Model (SDTM) level. Note though that the simple conversion to SI units does not represent a full homogenization of results from different local laboratories using different methods. To ensure full comparability, the observed laboratory results will be normalized to a unique set of standard reference ranges using the location-scale normalization formula (Chuang-Stein, 1992) which normalizes all results in relation to a standard set of reference ranges (for hematology, clinical chemistry and coagulation parameters):

$$s = L_S + (x - L_X) \frac{(U_S - L_S)}{(U_X - L_X)}$$

where:

s = normalized observed value

x = original observed value in SI units

L_S = Lower Limit of the reference range chosen to be the standard reference range

U_S = Upper Limit of the reference range chosen to be the standard reference range

L_X = Lower Limit of the reference range associated with the original observed value in SI units (local laboratory reference range)

U_X = Upper Limit of the reference range associated with the original observed value in SI units (local laboratory reference range)

This transformation preserves the distance of the original laboratory result from the lower limit of normal as a multiple of the specified standard reference range.

Note that the choice of the standard reference range is arbitrary, however, the most recent reference ranges used by ICON Central Laboratories (including the age and gender specific reference ranges for parameters, where available) will be used to normalize the results in this study.

Normalization of the laboratory results will be performed in the ADaM programming by ICON. All laboratory data (hematology, serum chemistry and coagulation) and changes from Baseline for numeric variables will be listed for participants who have at least one value outside of the reference range. All urinalysis data will be listed for all participants. Data will be listed by study participant, laboratory panel, laboratory parameter and visit within each treatment group. Any laboratory measurements that are BLQ or ALQ will be handled as described in [Section 4.2.2](#). For the relevant numeric laboratory parameters, the reference ranges supplied by the local analytical laboratory will be used to flag values outside the reference range as low or high in this listing. For the parameters for which the local laboratory cannot supply the reference ranges, the reference ranges provided by ICON Central Laboratories will be used instead. A listing of all laboratory results outside of the reference range will also be presented. The reference ranges will also be reported in the listings.

In addition, for the relevant laboratory tests, CTCAE severity grades (Grade 1, Grade 2, Grade 3, Grade 4) will be applied (where possible) in the ADaM programming according to NCI CTCAE Version 5.0, and these grades will also be listed for the relevant laboratory parameters. Note that Grade 0 will be applied in cases where a result is normal for the relevant laboratory test and Grade 5 is not applicable in the grading of laboratory data.

Observed values and changes from Baseline in the hematology, serum chemistry and coagulation parameters presented below in Table 8-1 will be summarized at each visit. In addition, for each of these parameters, the Baseline value, the minimum, maximum, average and last post-Baseline value for each participant will be summarized by cycle using descriptive statistics. These post-Baseline summary measures will be calculated based on all available scheduled postdose values within each cycle, i.e. from Day 8 of the current cycle up to Day 1 (predose) of the subsequent cycle. The last value in a cycle will be the predose value of the subsequent cycle where a subsequent cycle occurs, otherwise it will be the value at the last scheduled assessment. If only 1 value is available then the average will not be calculated and presented but this value will be used for the minimum, maximum and last post-Baseline summary measures. These summary measures for each cycle will also be listed.

For those laboratory parameters with a CTCAE toxicity assigned, shift tables for the change from Baseline in CTCAE severity grade at each visit and to the worst post-Baseline CTCAE severity grade during the Treatment Period will be presented.

This document cannot be used to support any marketing authorization
application and any extensions or variations thereof.

Table 8-1: Clinical Laboratory Assessments

Laboratory Assessment	Laboratory Parameters
Hematology	Platelet Count, RBC Count, Hemoglobin, Hematocrit, RBC Indices (MCV, MCH, MCHC), WBC Count with Differential (Absolute Neutrophils, Absolute Lymphocytes, Absolute Monocytes, Absolute Eosinophils, Absolute Basophils)
Clinical Chemistry	ALT, AST, ALP (including liver-specific ALP for use in assessing participants with bone metastases at Screening), Bicarbonate, Sodium, Potassium, Magnesium, Chloride, Calcium, Total Bilirubin, BUN or Urea, Serum Creatinine, Glucose (non-fasted), Phosphorus or Phosphate, Albumin, Total Protein, Uric Acid, Amylase, GGT, Cholesterol, Creatine Kinase, CRP, LDH, Lipase, Triglycerides
Coagulation	aPTT and either PT or INR
Routine Urinalysis	Specific Gravity, pH, Glucose, Protein, Blood, Ketones, Bilirubin, Urobilinogen, Nitrite, Leukocyte Esterase by Dipstick Microscopic Examination (if blood or protein is abnormal, including crystals)
Screening Tests	Pregnancy tests: FSH and estradiol (for women of non-childbearing potential only); serum or urine hCG pregnancy test (for women of childbearing potential) Bone turnover markers: blood BAP, blood CTx, urinary NTx and urinary CTxII Tumor markers: PSA, CA125, CA19-9

ALP=alkaline phosphatase; ALT=alanine aminotransferase; aPTT=activated partial thromboplastin time; AST=aspartate aminotransferase; BAP=bone alkaline phosphatase; BUN=blood urea nitrogen; CA=cancer antigen; CRP=C-reactive protein; CTx=C-terminal telopeptide; FSH=follicle-stimulating hormone; GGT=gamma glutamyl transferase; hCG=human chorionic gonadotropin; INR=international normalized ratio; LDH=lactate dehydrogenase; MCH=mean corpuscular hemoglobin; MCHC=mean corpuscular hemoglobin concentration; MCV=mean corpuscular volume; NTx=N-terminal telopeptide; PSA=prostate specific antigen; PT=prothrombin time; RBC=red blood cell; WBC=white blood cell.

The screening laboratory tests included above in Table 8-1 will be listed only.

Liver function abnormalities will be defined using the following criteria:

- ALT or AST $\geq 2 \times \text{ULN}$
- ALT or AST $\geq 3 \times \text{ULN}$
- Total bilirubin $\geq 2 \times \text{ULN}$
- Total bilirubin $\geq 3 \times \text{ULN}$
- ALT or AST $\geq 5 \times \text{ULN}$
- ALT or AST $\geq 8 \times \text{ULN}$
- ALT or AST $\geq 3 \times \text{ULN}$ AND total bilirubin $\geq 2 \times \text{ULN}$ ($>35\%$ direct bilirubin)

For the subgroups of participants with liver metastases and without liver metastases at Baseline, the number and percentage of participants in each liver function abnormality category will be summarized at each visit.

In addition, participants with potential drug induced liver injury (PDILI) criteria are those that fulfill the following laboratory data (based on liver function tests) criteria at a visit:

- AST or ALT and total bilirubin within the normal range at Baseline and AST or ALT $\geq 3\times$ ULN concurrent with total bilirubin $\geq 2\times$ ULN;
- AST, ALT or total bilirubin above ULN at Baseline and AST or ALT ≥ 2 times Baseline values AND AST or ALT $\geq 3\times$ ULN (participants without liver metastases at Baseline)/AST or ALT $\geq 8\times$ ULN (participants with liver metastases at Baseline) concurrent with total bilirubin above ULN at Baseline and total bilirubin ≥ 2 times Baseline value or $\geq 3\times$ ULN (whichever is lower).

All relevant laboratory data collected for participants with a PDILI event (i.e. liver function tests) will be listed at the visits at which at least one of the above criteria was fulfilled.

The number and percentage of participants meeting different combinations of the ALT, AST and total bilirubin criteria defined above will be summarized by treatment group. This summary will be presented for all participants as well as for the subgroups of participants who had liver metastases at Baseline and participants without liver metastases at Baseline.

A separate listing will also be produced containing DILI-relevant family medical history, lifestyle data (alcohol consumption or drug abuse in the previous 6 months), hepatic event supplemental medical history and any hepato-toxic medications taken for participants in the SS with a PDILI event.

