8.3 Clinical laboratory evaluations

Laboratory tests will be performed at the Screening visit, predose on UCB6114 dosing visits (Days 1 and 15 of each cycle for participants in Cohorts 1 and 2 and on Day 1 of each cycle for participants in Cohorts 3 and 4) and at the SFU visit. In addition, participants in Cohort 4 will have laboratory tests performed on non-dosing Day 15 of Cycle 1 and 2 only.

Due to the use of multiple local laboratories (1 per site in the UK and US) in Part A1 of this study, results will potentially be recorded in different units and with reference to different normal ranges. Further, for some laboratory tests, different normal ranges will be applied to males and females and age groups. As a first step to ensure comparability of laboratory results, results and

normal ranges will be converted to the same International System of Units (SI) units using UCB's standard conversion factors. This will be programmed at the Study Data Tabulation Model (SDTM) level. Note though that the simple conversion to SI units does not represent a full homogenization of results from different local laboratories using different methods. To ensure full comparability, the observed laboratory results will be normalized to a unique set of standard reference ranges (for hematology, clinical chemistry and coagulation parameters) using the location-scale normalization formula (Chuang-Stein, 1992).

$$s = L_S + (x - L_X) \frac{(U_S - L_S)}{(U_X - L_X)}$$

and when the standard lower limit is 0: $s = x \frac{U_S}{U_X}$ where:

s = normalized observed value

x = original observed value in SI units

LS = Lower Limit of the reference range chosen to be the standard reference range

US = Upper Limit of the reference range chosen to be the standard reference range

LX = Lower Limit of the reference range associated with the original observed value in SI units (local laboratory reference range)

UX = Upper Limit of the reference range associated with the original observed value in SI units (local laboratory reference range)

This transformation preserves the distance of the original laboratory result from the lower limit of normal as a multiple of the specified standard reference range.

Note that the choice of the standard reference range is arbitrary, however, the most recent reference ranges used by ICON Central Laboratories (including the age and gender specific reference ranges for parameters, where available) will be used to normalize the results in this study.

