Normalization of the laboratory results will be performed in the ADaM programming by ICON.

All laboratory data (hematology, serum chemistry and coagulation) and changes from Baseline for numeric variables will be listed for participants who have at least one value outside of the reference range. All urinalysis data will be listed for all participants. Data will be listed by study participant, laboratory panel, laboratory parameter and visit within each treatment group. Any laboratory measurements that are BLQ or ALQ will be handled as described in [Section 4.4](#). For the relevant numeric laboratory parameters, the reference ranges supplied by the local analytical laboratory will be used to flag values outside the reference range as low or high in this listing. For the parameters for which the local laboratory cannot supply the reference ranges, the reference ranges provided by ICON Central Laboratories will be used instead. A listing of all laboratory results outside of the reference range will also be presented. The reference ranges will also be reported in the listings.

In addition, for the relevant hematology, clinical chemistry and coagulation laboratory tests, CTCAE severity grades (Grade 1, Grade 2, Grade 3, Grade 4) will be applied (where possible) in the ADaM programming according to NCI CTCAE Version 5.0, and these grades will also be listed for the relevant laboratory parameters. Note that Grade 0 will be applied in cases where a

result is normal for the relevant laboratory test and Grade 5 is not applicable in the grading of laboratory data.

Observed values and changes from Baseline in the hematology, serum chemistry and coagulation parameters presented below in [Table 8-1](#) will be summarized at each visit.

The summaries of normalized hematology, serum chemistry and coagulation values and changes from Baseline may be presented by tumor type (CRC, Gastric/GEJ-Cancer and Pancreatic Adenocarcinoma) depending on the number of participants with specific tumor types.

For those laboratory parameters with a CTCAE toxicity assigned, shift tables for the change from Baseline in CTCAE severity grade at each visit will be presented.

Table 8-1: Clinical Laboratory Assessments

Laboratory Assessment	Laboratory Parameters
Hematology	Platelet Count, RBC Count, Hemoglobin, Hematocrit, RBC Indices (MCV, MCH, MCHC), WBC Count with Differential (Absolute Neutrophils, Absolute Lymphocytes, Absolute Monocytes, Absolute Eosinophils, Absolute Basophils)

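### The laboratory normalization formula in section 8.3 has no lower bound, so some pairs of reference ranges give negative results, and Part A lacks the zero-lower-limit rule that Part A1 has

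*SAP*

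**What the plan says.** Part A explains why results need harmonizing: "The use of multiple local laboratories (1 per site in the UK) in Part A of this study has meant that results have been recorded". Units and normal ranges vary between those laboratories. After conversion to SI units, "To ensure full comparability, the observed laboratory results will be normalized to a unique set of standard reference ranges using the location-scale normalization formula". The printed formula is s = L_S + (x - L_X)(U_S - L_S)/(U_X - L_X), where X marks the local range and S the standard range. The standard limits are "the most recent reference ranges used by ICON Central Laboratories", with no values printed. The property claimed is: "This transformation preserves the distance of the original laboratory result from the lower limit of normal as a multiple of the specified standard reference range".

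Part A1 section 8.3 prints the same formula and adds a second one, "and when the standard lower limit is 0": s = x·U_S/U_X. Part A has no such case.

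On use, "Normalization of the laboratory results will be performed in the ADaM programming by ICON". Part A then summarizes observed values and changes from Baseline by visit, and adds that "the minimum, maximum, average and last post-Baseline value for each participant will be summarized by cycle using descriptive statistics". Part A1 is more explicit about the input: "The summaries of normalized hematology, serum chemistry and coagulation values and changes from Baseline may be presented by tumor type".

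Three neighbouring rules matter. Low and high flags use the local laboratory's range (section 8.3). Safety results below quantification are set to half the LLOQ (Part A section 4.2.2; Part A1 section 4.4). Section 3.1 restricts confidence limits to possible values, but places no such restriction on the data.

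**The concern.** A linear map fixed only by the two reference limits can go below zero for results well under the lower limit. A negative platelet or neutrophil count is impossible, and it would come from the lowest results, which matter most for safety. It would enter visit means and SDs, the Part A per-cycle minima, and changes from Baseline. A result below quantification, first set to a positive half-LLOQ, could also be turned negative.

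The same map changes ratios to the upper limit. Section 8.3 defines liver criteria from 2x to 8x ULN and applies CTCAE grades in ADaM, the dataset layer where normalization is done. It does not say which value feeds them. Two competent programmers could therefore produce different counts at a given ULN threshold.

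**Working it through.** The plan states no figure to reproduce. The formula comes from section 8.3. **All numeric ranges below are assumptions**, because the SAP prints none.

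**Check of the claimed property.** x = L_X gives L_S and x = U_X gives U_S. The property holds as stated.

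**Where s falls below zero.** Solving s < 0 gives x < L_X - L_S(U_X - L_X)/(U_S - L_S). This cut-off is above 0 exactly when U_S/L_S > U_X/L_X.

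- Platelets, local 150-400, standard 140-450: slope 310/250 = 1.24; cut-off 150 - 140/1.24 = 37. x = 30 gives 140 - 120 × 1.24 = -8.8.
- Neutrophils, local 2.0-7.5, standard 1.8-8.0: cut-off 0.40; x = 0.3 gives -0.12.
- Lymphocytes, local 1.0-3.0, standard 0.8-4.0: slope 1.6; cut-off 1.0 - 0.8/1.6 = 0.5.

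**Reverse case.** Neutrophils, local 1.5-8.0, standard 2.0-7.0: nothing goes negative, but x = 0.5 gives 2.0 - 1.0 × 5.0/6.5 = 1.23, and x = 0 gives 0.85. Severe neutropenia is understated.

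**Equal ratios.** Neutrophils, local 2.0-7.0, standard 1.8-6.3: x = 0 gives 0 and x = 0.5 gives 0.45. There is no distortion.

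**Standard lower limit of 0 in Part A.** This step needs no assumed numbers. With L_S = 0 the formula becomes s = (x - L_X)·U_S/(U_X - L_X). If L_X > 0, every x below L_X gives a negative s. Under the Part A1 rule the same result is x·U_S/U_X, which cannot be negative. If L_X is also 0, the two forms are identical.

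**Multiples of ULN.** For x = k·U_X, s/U_S = 1 + (k - 1)·[(U_S - L_S)/U_S]/[(U_X - L_X)/U_X]. This equals k only if k = 1 or L_S/U_S = L_X/U_X, which includes both lower limits being 0. For ALT at a true 3x ULN:

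| Local | Standard | Multiple after normalization |
|---|---|---|
| 0-40 | 10-50 | 2.60 |
| 10-50 | 5-40 | 3.19 |
| 10-40 | 0-40 | 3.67 (Part A); 3.00 under the Part A1 rule |
| 8-40 | 10-50 | 3.00 |

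**How often.** This cannot be derived. With local and standard neutrophil limits drawn from the same assumed spread (lower 1.5-2.2, upper 6.3-8.0), a negative value is possible for about 50% of range pairs. That is a share of range pairs. It is not a share of results or participants.

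**Which value is summarized.** Part A section 8.3 defines s as a normalized observed value and then summarizes observed values. Part A1 section 8.3 calls its summaries normalized. If the summaries did not use s, the normalization would have no stated purpose.

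**The case against.** The algebra is not in dispute; the objections concern reach.

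A reader might infer that the safety laboratory summaries are wrong for participants with the deepest cytopenias. The documents do not show that. Negatives need both an unfavourable range pair and a result below the cut-off, and no limits are printed. A reader might also infer that every ULN multiple is altered. It is not: 1x never changes, and none changes when the L/U ratios match or both lower limits are 0. Nor do Parts A and A1 always differ when the standard lower limit is 0; they differ only if the local one is not 0.

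The most tempting inference is that grades and liver criteria are misclassified. Sharing the ADaM layer does not mean sharing an input. No section says CTCAE grades, liver criteria, PDILI or Hy's Law are computed on s, and the only stated out-of-range basis, for the low and high flags, is local.

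Low results also stay visible elsewhere: in the flags, the listing of out-of-range results and the grade shift tables. The primary endpoints are TEAEs and DLTs, and laboratory data are other safety endpoints.

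All of this stands and limits the point. It does not remove it. The printed formula can give impossible values, the reverse range pairs bring a different distortion, and Part A omits a safeguard that Part A1 contains.

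**Conclusion.** The point holds in a conditional form. Section 8.3 fixes a transformation with no lower bound in both parts. It yields negative values for sufficiently low results when U_S/L_S > U_X/L_X, and inflates very low counts in the reverse case. In Part A it makes every result below the local lower limit negative when L_S = 0 and L_X > 0. That last statement needs no assumed limits, only that such a range pair occurs.

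The affected outputs are descriptive: visit summaries, changes from Baseline and, in Part A, per-cycle minima. This assumes that the summaries use s, which the text indicates without quite saying so for Part A. The size is known only for illustrative ranges, and the frequency is unknown.

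The basis for CTCAE grades, ULN multiples, PDILI and Hy's Law is a missing clarification; no misclassification is demonstrated. The change should be made because it is cheap and the outputs are safety tables.

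**What to change.** 1. In Part A, add the Part A1 rule: s = x·U_S/U_X when L_S = 0.
2. In both SAPs, add a rule that keeps s non-negative when L_S > 0. One option keeps the printed formula for x ≥ L_X and uses s = x·L_S/L_X for x < L_X. It equals L_S at x = L_X and is never negative; the platelet count of 30 above becomes 30 × 140/150 = 28. The other option is the scale-only form s = x·U_S/U_X throughout, which also preserves ULN multiples; the same count becomes 30 × 450/400 = 33.75.
3. As a clarification, state that CTCAE grades, shift tables, liver ULN criteria, PDILI and Hy's Law use the SI value with the local reference range. State also that the descriptive summaries use s, if that is the intention.

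The cost is SAP wording and a small ADaM change, with no new data. The claimed distance-from-lower-limit property is lost wherever the new rule applies, so that sentence needs amending. The piecewise option changes slope at the lower limit, so a change from Baseline that crosses it mixes two scales, and it does not restore ULN multiples. The scale-only option no longer maps the local lower limit to the standard one: 150 becomes 168.75 in the platelet example, against a standard lower limit of 140.

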8.2.1 Adverse events of special interest

An AESI is any AE that a regulatory authority has mandated be reported on an expedited basis, regardless of the seriousness, expectedness, or relatedness of the AE to the administration of a UCB product/compound.

For ONC001, potential Hy's Law is used to identify AESIs and is defined using the laboratory data and the following potential drug-induced liver injury (PDILI) criteria:

- $\geq 3x$ upper limit of normal (ULN) alanine aminotransferase (ALT) *or* aspartate aminotransferase (AST) with coexisting $\geq 2x$ ULN total bilirubin in the absence of $\geq 2x$ ULN alkaline phosphatase (ALP), with no alternative explanation for the biochemical abnormality;
- Study participants who have evidence of liver metastases may be considered to have an alternate etiology for the described laboratory abnormalities.

All AESIs will be flagged on the listing of AEs.

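### Section 8.3's two PDILI criteria cannot flag a participant whose AST and ALT are both raised, and bilirubin normal, at Baseline

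*SAP*

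**What the plan says.** Section 8.3 of the Part A SAP defines a PDILI participant by two alternative criteria, applied visit by visit.

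- **Criterion 1** starts from "AST or ALT and total bilirubin within the normal range at Baseline" and then looks for AST or ALT at least 3x ULN together with bilirubin at least 2x ULN.
- **Criterion 2** starts from "AST, ALT or total bilirubin above ULN at Baseline and AST or ALT" at least 2x Baseline. AST or ALT must also reach 3x ULN (no liver metastases at Baseline) or 8x ULN (liver metastases). All this must be "concurrent with total bilirubin above ULN at Baseline and total bilirubin" at or above the lower of 2x Baseline and 3x ULN.

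Liver tests for a participant with a PDILI event "will be listed at the visits at which at least one of the above criteria was fulfilled". A separate listing brings together family history, lifestyle data, supplemental hepatic history and hepatotoxic medications for participants with a PDILI event. Section 8.3 of the Part A1 SAP repeats both criteria and both listings.

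Section 8.2.1 of each SAP has a further rule, potential Hy's Law, which "is defined using the laboratory data and the following potential drug-induced liver injury (PDILI) criteria": ALT or AST at least 3x ULN with bilirubin at least 2x ULN, ALP not at or above 2x ULN, and no alternative explanation. It sets no Baseline condition. It adds: "Study participants who have evidence of liver metastases may be considered to have an alternate etiology".

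**The concern.** The opening of criterion 2 deliberately lets in participants whose only Baseline abnormality is a raised transaminase. Its bilirubin condition then shuts out everyone with normal Baseline bilirubin. The mention of AST and ALT in the opening therefore has no effect, which suggests a drafting slip rather than a choice. The SAP itself expects abnormal livers at entry, since it sets a separate transaminase limit for participants with liver metastases.

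At stake is who appears in the PDILI visit listing and the consolidated hepatic listing. The second gathers the background a reader would want when judging whether a liver event is due to the drug. Section 8.3 and Section 8.2.1 also both call their rules PDILI criteria, yet they disagree for this group.

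**Working it through.** There is no planned figure to reproduce. The check is whether each Baseline pattern can ever satisfy a criterion.

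**Baseline patterns against the criteria as written**

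| AST and ALT at Baseline | Bilirubin at Baseline | Criterion 1 | Criterion 2 |
|---|---|---|---|
| both normal | normal | can be met | entry fails |
| one raised | normal | can be met if one normal transaminase is enough; cannot if both must be normal | entry met, bilirubin condition cannot be met |
| both raised | normal | cannot be met | entry met, bilirubin condition cannot be met |
| any | raised | cannot be met | can be met |

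The third row is the gap. The second row joins it if criterion 1 means that both transaminases must be normal.

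**Grid check of the third row.** Baseline AST and ALT were each set to 1.5 or 2.5x ULN and bilirubin to 0.3 or 0.8x ULN: 2 x 2 x 2 = 8 starting points. On-treatment AST and ALT each took seven values from 0.8 to 40x ULN, and bilirubin seven values from 0.8 to 10x ULN: 7 x 7 x 7 = 343 outcomes. That gives 8 x 343 = 2744 combinations, run with and without liver metastases.

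- Flagged by either criterion: 0 of 2744 without metastases and 0 of 2744 with them.
- Combinations with ALT or AST at least 3x ULN and bilirubin at least 2x ULN: 45 of the 49 transaminase pairs x 5 of the 7 bilirubin values x 8 starting points = 1800 in each group.

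These counts show that the rule cannot fire. They are not estimates of how often injury occurs.

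**Two cases side by side, no liver metastases (multiples of ULN)**

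| | Baseline | On treatment | Result |
|---|---|---|---|
| Case A | ALT 1.5, bilirubin 1.1 | ALT 3, bilirubin 2.2 | Criterion 2 met: 3 is 2 x 1.5 and reaches 3; 2.2 reaches the lower of 2 x 1.1 = 2.2 and 3 |
| Case B | ALT 1.5, AST 1.2, bilirubin 0.8 | ALT 9, bilirubin 4 | Criterion 1 fails on Baseline transaminases; criterion 2 fails on Baseline bilirubin |

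The case with the larger rise is the one left out.

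**Alternative reading of criterion 2.** If the 3x ULN bilirubin limit is detached from the Baseline-bilirubin requirement and stands alone, 1026 of 2744 combinations are flagged without metastases and 792 of 2744 with them. That reading is hard to hold, because the text takes the lower of 2x Baseline and 3x ULN as one threshold.

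**The case against.** The strongest reply is that little is hidden. Most of it stands:

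- Section 8.3 lists all hematology, chemistry and coagulation data for anyone with at least one out-of-range value. Everyone in this group has raised AST and ALT at Baseline, so all their liver tests are listed.
- The liver function abnormality categories in Section 8.3 have no Baseline condition. Case B enters all four ALT/AST categories and both bilirubin categories; the combined category also depends on direct bilirubin.
- Case B meets the ALT and bilirubin limits of potential Hy's Law in Section 8.2.1. It would be flagged there unless ALP is at least 2x ULN or another explanation, such as liver metastases, is accepted.
- Medical history and all medications are listed regardless of PDILI status (Sections 6.5 and 6.6).

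A reader might infer that liver injury in this group goes unseen, or that the primary safety result is understated. The documents do not support either. The routes above remain open, and the primary endpoints in Section 2.2.1.1 are TEAEs and DLTs, neither defined through the Section 8.3 criteria.

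The reply does not repair the rule. Potential Hy's Law carries ALP and alternative-cause exclusions that Section 8.3 lacks, so it is not a full substitute, and the consolidated hepatic listing depends on a PDILI event.

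**Conclusion.** The point holds as a fault in the Section 8.3 definition, in both SAPs. A participant with AST and ALT both above ULN and bilirubin normal at Baseline cannot meet either criterion. If criterion 1 requires both transaminases to be normal, the same is true with only one raised. The loss is the Section 8.3 flag, the PDILI visit listing and the consolidated hepatic listing.

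This rests on reading criterion 2's bilirubin condition as one joint requirement, which its wording favors. A reader might also be tempted to put a headcount on it. The SAP gives no frequency for this Baseline pattern, and such a count would in any case be of people who could be missed, not of missed injuries. Nor does the SAP say that raised ALP or liver metastases are common in this group, so how often potential Hy's Law would also fail to flag a case is unknown.

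**What to change.** In Section 8.3 of both SAPs:

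1. Reconcile the entry condition of criterion 2 with its bilirubin condition, so that every Baseline pattern of AST, ALT and bilirubin can be evaluated under at least one criterion. Overlap between the criteria is harmless, because meeting either one sets the flag.
2. State whether criterion 1 needs either transaminase or both to be normal at Baseline.
3. Reconcile the Section 8.3 criteria with the rule in Section 8.2.1 that carries the same PDILI label, or name the two differently and say which output uses which.

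The thresholds are for the sponsor's clinical team to set. The cost is about one sentence on criterion 2 in each SAP, short clarifications for items 2 and 3, and one changed programming condition. No new data are needed.
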